10.5.2 Physical Examination

All data collected at the physical examination performed at the Screening visit will be listed.

10.5.3 Pregnancy Tests

Pregnancy test results will be listed together with female fertility status.

11 Pharmacokinetics

Analyses of the pharmacokinetics exploratory endpoints including the presence of EDP1815 in stool and/or blood using PCR primers will be addressed in a separate analysis plan and will not be further discussed in this document.

12 Reporting Conventions

When reporting relative frequencies or other percentage values, the following rules apply:

- For values where all subjects fulfil certain criteria, the percentage value will be displayed as 100
- For values where the absolute frequency is 0, there will be no percentage presented at all
- All other percentage displays will use 1 decimal place

When reporting descriptive statistics, the following rules will apply in general:

- n will be an integer
- Mean and median will use 1 decimal place more than the original data
- Standard deviation will use 2 decimal places more than then original data
- Minimum and maximum will be reported using the same number of decimal places as the original value

- If no subjects have data at a given timepoint, for example, then only n=0 will be presented. However, if n<3, present the n, min and maximum only. If n=3, n, mean, median, minimum and maximum will be presented only. The other descriptive statistics will be left blank

Where reporting estimated statistics from inferential tests and models, the following rules will apply in general:

- P-values ≥ 0.001 will be reported to 3 decimal places; p-values less than 0.001 will be reported as "<0.001".
- Estimated parameters and 95% confidence intervals on the same scale as raw observations will be reported to 1 decimal place more than the original data, standard errors will be reported to decimal places more
- Estimated parameters and 95% confidence intervals of percentage change variables will be reported to 2 decimal places, standard errors will be reported to 3 decimal places
- Estimated parameters and 95% confidence intervals, not on the same scale as raw observations or for percentage change statistics (e.g. regression coefficients) will be reported to 3 significant figures, standard errors will be reported to one further decimal place.

13 Technical Details

Statistical evaluation will be performed by [REDACTED].

CDISC standards will not be used for this study. The analysis datasets will be produced using a similar structure to those described for the analysis dataset model (ADaM) but will be not be fully validated and will be programmed directly from the source CRF and external data rather than from SDTM datasets.

All analyses will be performed using SAS version 9.2 or higher (SAS Institute, Cary, NC, USA).

14 Summary of Changes to the Protocol

Not applicable.

15 References

Fine, J. a. (1999). A Proportional Hazards Model for the Subdistribution of a Competing Risk. *Journal of American Statistics Association*, 94(446), 496-509.

16 Appendix 1: List of Tables, Figures and Listings

All outputs detailed in the following sections will be produced for the final analysis. Programming notes also indicate where tables will be produced for interims using the following abbreviations:

DMC-Blinded – produced as a blinded output with only the overall column shown - all DMC meetings

DMC-Unblinded – produced as an unblinded output – all DMC meetings

DMC-Safety – produced as an unblinded output – all DMC meetings after participants aged >65 years have been approved for inclusion

DMC-Efficacy – produced as an unblinded output – DMC meeting after 60 participants have completed 21 days treatment only

Note that some outputs will only be produced if the criterion specified in the programming notes is met.

Highlighted **XXXXX** text indicates that the full title is dependent on currently unknown factors (e.g. name of medications which becomes SOC during the study).

If the study is stopped early, outputs will be produced as specified in Early Stop column.

16.1 Study Population

16.1.1 Tables

Number	Title	Population	Early Stop	Programming notes ¹
14.1.1.1	Summary of Disposition	ITT	Yes	DMC-Blinded, DMC-Unblinded
14.1.1.2	Summary of Screening Status	Enrolled	Yes	DMC-Blinded
14.1.1.3	Summary of Participants by Site	ITT	Yes	
14.1.1.4	Summary of Data Availability at Each Study Day by Inpatient/Outpatient Status	ITT	Yes	
14.1.1.5	Summary of Important Protocol Deviations	ITT	Yes	
14.1.1.6	Summary of Populations	Enrolled	Yes	
14.1.2.1	Summary of Demographic Details	ITT	Yes	DMC-Unblinded
14.1.2.2	Summary of Smoking Status	ITT	Yes	
14.1.2.3	Summary of Baseline Disease Characteristics	ITT	Yes	

Number	Title	Population	Early Stop	Programming notes ¹
14.1.3.1	Summary of Potential Risk Factors for Severe Illness with COVID-19	ITT	Yes	DMC-Unblinded
14.1.3.2	Summary of Past Medical History	ITT	Yes	
14.1.3.3	Summary of Current Medical History	ITT	Yes	
14.1.4.1	Summary of Prior Medications	ITT	Yes	
14.1.4.2	Summary of All Concomitant Medications for COVID-19	ITT	Yes	DMC-Unblinded
14.1.4.3	Summary of Concomitant Medications for COVID-19 Started Pre-treatment	ITT	Yes	
14.1.4.4	Summary of Concomitant Medications for COVID-19 Started During the Treatment Phase	ITT	Yes	
14.1.4.5	Summary of Concomitant Medications for COVID-19 Started During the Follow-Up Phase	ITT	Yes	
14.1.4.6	Summary of All Concomitant Medications not for COVID-19	ITT	Yes	
14.1.4.7	Summary of Concomitant Medications not for COVID-19 Started Pre-treatment	ITT	Yes	
14.1.4.8	Summary of Concomitant Medications not for COVID-19 Started During the Treatment Phase	ITT	Yes	
14.1.4.9	Summary of Concomitant Medications not for COVID-19 Started During the Follow-Up Phase	ITT	Yes	
14.1.5.1	Summary of Treatment Compliance	Safety	Yes	DMC-Blinded, DMC-Unblinded
14.1.5.2	Summary of Daily Diary Compliance After Discharge	ITT	Yes	
14.1.6	Summary of Exposure to Study Medication	Safety	Yes	DMC-Unblinded

16.2 Efficacy

16.2.1 Tables

Number	Title	Population	Early Stop	Programming notes ¹
14.2.1.1	Summary of Change from Baseline in Trough S/F Ratio in Days 1-14	ITT	Yes	DMC-Efficacy
14.2.1.2.1	Analysis of Change from Baseline in Trough S/F Ratio in Days 1-14	ITT		DMC-Efficacy

Number	Title	Population	Early Stop	Programming notes ¹
14.2.1.2.2	Analysis of Change from Baseline in Trough S/F ratio in Days 1-14, Sensitivity Analysis with No Imputation of Trough S/F Ratio for Participants Who Die	ITT		DMC-Efficacy
14.2.1.2.3	Analysis of Change from Baseline in Trough S/F Ratio in Days 1-14, Sensitivity Analysis Accounting for Use of New SOC Before Day 14	ITT		DMC - Efficacy Only produced if a new SOC is introduced during the study
14.2.1.2.4	Analysis of Change from Baseline in Trough S/F Ratio in Days 1-14, by Use of Use of New SOC Before Day 14	ITT		DMC-Efficacy Only produced if a new SOC is introduced during the study and shows significant interaction with EDP1815
14.2.2.1.1	Summary of Change from Baseline in S/F Ratio at days 4, 7, 10 and 14, No Imputation	ITT	Yes	DMC-Efficacy
14.2.2.1.2	Summary of Change from Baseline in S/F ratio at days 4, 7, 10 and 14, With Imputation Applied	ITT		DMC-Efficacy
14.2.2.2.1	Analysis of Change from Baseline in S/F Ratio at Days 4, 7, 10 and 14	ITT		DMC-Efficacy
14.2.2.2.2	Analysis of Change from Baseline in S/F Ratio at Days 4, 7, 10 and 14, Sensitivity Analysis with No Imputation of S/F Ratio for Participants Who Die	ITT		DMC-Efficacy
14.2.2.2.3	Analysis of Change from Baseline in S/F Ratio at Days 4, 7, 10 and 14, Sensitivity Analysis Using MMRM approach	ITT		Only produced if >10% drop-out before D14
14.2.2.2.4	Analysis of Change from Baseline in S/F ratio at Days 4, 7, 10 and 14, Sensitivity Analysis Accounting for Use of New SOC	ITT		Only produced if a new SOC is introduced during the study
14.2.3.1.1	Summary of Percentage Change from Baseline in S/F ratio at days 4, 7, 10 and 14, No imputation	ITT	Yes	DMC-Efficacy
14.2.3.1.2	Summary of Percentage Change from Baseline in S/F ratio at days 4, 7, 10 and 14, With imputation applied	ITT		DMC-Efficacy

Number	Title	Population	Early Stop	Programming notes ¹
14.2.3.2.1	Analysis of Percentage Change from Baseline in S/F Ratio at Days 4, 7, 10 and 14	ITT		DMC-Efficacy
14.2.3.2.2	Analysis of Percentage Change from Baseline in S/F Ratio at Days 4, 7, 10 and 14, Sensitivity Analysis with No Imputation of S/F Ratio for Participants Who Die	ITT		DMC-Efficacy
14.2.3.2.3	Analysis of Percentage Change from Baseline in S/F Ratio at Days 4, 7, 10 and 14, Sensitivity Analysis Using MMRM approach	ITT		Only produced if >10% drop-out before D14
14.2.3.2.4	Analysis of Percentage Change from Baseline in S/F ratio at Days 4, 7, 10 and 14, Sensitivity Analysis Accounting for Use of New SOC	ITT		Only produced if a new SOC is introduced during the study
14.2.4.1	Summary and Analysis of WHO OSCI score at Days 4, 7, 14, 21 and 42	ITT	Yes, summary only	DMC-Unblinded
14.2.4.2	Shift Table of Changes from Baseline in WHO OSCI Score at Days 4, 7, 14, 21 and 42	ITT	Yes	DMC-Unblinded
14.2.4.3	Summary of Participants Remaining at or Below Their Baseline WHO OSCI Scale Score at Days 4, 7, 14, 21 and 42	ITT	Yes	DMC-Efficacy
14.2.4.4	Summary and Analysis of Maximum WHO OSCI Score Reported	ITT	Yes, exclude p-value	DMC-Efficacy
14.2.5.1	Summary and Analysis of Overall Survival	ITT	Yes, exclude Hazard ratio, CI and p-value	DMC-Efficacy
14.2.5.2	Summary and Analysis of Overall Survival, Sensitivity Analysis Accounting for Use of New SOC	ITT		
14.2.6.1	Summary and Analysis of Intubation and Mechanical Ventilation Free Survival	ITT	Yes, exclude Hazard ratio, CI and p-value	DMC-Efficacy

Number	Title	Population	Early Stop	Programming notes ¹
14.2.6.2	Summary and Analysis of Intubation and Mechanical Ventilation Free Survival, Sensitivity Analysis Accounting for Use of New SOC	ITT		
14.2.7	Summary and Analysis of Time to Discharge	ITT	Yes, exclude Hazard ratio, CI and p-value	DMC-Efficacy
14.2.8	Summary and Analysis of Time to SpO ₂ ≥94% on Room Air Without Further Requirement for Oxygen Therapy	ITT	Yes, exclude Hazard ratio, CI and p-value	DMC-Efficacy
14.2.9	Summary and Analysis of Time to Recovery from Onset of Symptoms	ITT	Yes, exclude Hazard ratio, CI and p-value	DMC-Efficacy
14.2.10	Summary of Number of Days Requiring Oxygen Therapy	ITT	Yes	DMC-Efficacy
14.2.11	Summary of Number of Days with Pyrexia	ITT	Yes	DMC-Efficacy
14.2.12	Summary of Maximum Daily Temperature	ITT	Yes	DMC-Efficacy
14.2.13	Summary of Maximum and Minimum Daily SpO ₂ values	ITT	Yes	DMC-Efficacy
14.2.14	Summary of Change from Baseline in Cytokine levels at Days 4 and 7	ITT		
14.2.15	Summary of Change from baseline in Inflammatory Response Markers at Days 4 and 7	ITT	Yes	
14.2.16	Exploratory Analysis of Potential Predictor-Treatment Interactions	ITT		

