9.1.1.1 Early Stopping

In the case of stopping the study early due to low recruitment, no inferential efficacy analysis will be carried out. Figures will not be presented. Only summaries and listings of the study population, primary and secondary efficacy endpoints, and safety data will be produced.

The list of outputs produced in case of early stopping of the study is provided in Appendix 1: List of Tables, Figures and Listings.

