9.3 Secondary Efficacy Analyses

9.3.1 Change from Baseline in S/F Ratio

9.3.1.1 Estimands

The endpoints will be the change from baseline in S/F ratio as measured on Days 4, 7, 10 and 14. The population summary measure of interest will be the difference in mean change from baseline in S/F ratio between EDP1815 and placebo at the relevant study day.

The intercurrent event strategy for these estimands is described in [Table 10](#).

Table 10 Intercurrent Event Strategies for the Change from Baseline in S/F Ratio Secondary Estimands

Intercurrent event	Strategy to account for intercurrent event
Death prior to the study day of interest	Composite S/F ratio will be imputed as 0
Discharge prior to the study day of interest	Composite Last S/F ratio prior to discharge will be used. Participants will be assumed to remain above this value after discharge.
Treatment discontinuation before the study day of interest without withdrawal from the study	Treatment policy The actual S/F ratio reported at the timepoint will be used regardless of treatment discontinuation
Withdrawal from the study prior to the study day of interest.	While-on-treatment Participants will be excluded from the analysis at that study day

Data missing for reasons other than an intercurrent event will be imputed as defined in [Table 5](#).

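### After an early stop for low recruitment, the by-day S/F summaries are kept only without imputation, so for these two secondary endpoints they cover only participants alive and in hospital

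*SAP*

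**What the plan says.** - **Early-stop scope.** SAP 9.1.1.1 states: "In the case of stopping the study early due to low recruitment, no inferential efficacy analysis will be carried out". It drops the figures and adds: "Only summaries and listings of the study population, primary and secondary efficacy endpoints, and safety data will be produced".
- **Governing rule.** The introduction to SAP Section 16 (Appendix 1) says: "If the study is stopped early, outputs will be produced as specified in Early Stop column".
- **Rows marked Yes (SAP 16.2.1).** Table 14.2.2.1.1, "Summary of Change from Baseline in S/F Ratio at days 4, 7, 10 and 14, No Imputation", and Table 14.2.3.1.1, "Summary of Percentage Change from Baseline in S/F ratio at days 4, 7, 10 and 14, No imputation".
- **Rows left blank (SAP 16.2.1).** Table 14.2.2.1.2, "Summary of Change from Baseline in S/F ratio at days 4, 7, 10 and 14, With Imputation Applied", and Table 14.2.3.1.2, "Summary of Percentage Change from Baseline in S/F ratio at days 4, 7, 10 and 14, With imputation applied".
- **Endpoint definition.** SAP 9.3.1.1, Table 10, counts a participant who has died as S/F 0. For a participant already discharged it says: "Last S/F ratio prior to discharge will be used". SAP 9.3.2 handles percentage change in the same way. Table 5 turns these rules into imputations.
- **Full analysis.** SAP 9.3.1.2 plans both an unimputed and an imputed summary. It also says that data missing through death or discharge cannot be treated as missing at random.

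**The concern.** SpO2 is not measured after discharge (SAP 5.3.3.6), and the dead have no reading. An unimputed S/F table for Day 4, 7, 10 or 14 therefore describes only those alive and in hospital on that day. Who belongs to that group depends on what happened after randomization, and treatment may affect it.

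The early-stop report would thus present change and percentage change in S/F for a selected remainder. That is not how Table 10 defines these endpoints, and the SAP itself says this missingness is not ignorable. If the arms differ in deaths or discharges, the kept tables can look alike although the endpoint as defined differs. In a small stopped trial they may also be nearly empty by Day 14.

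**Working it through.** **The plan's own figure.** The plan gives no figure on this point. Its only design figure, SAP Table 8, concerns trough S/F and is not in dispute. It reproduces as t(0.975, N−2) × SD × √(4/N). For N = 60 and SD 100 this gives 51.7, as printed, and all 18 cells agree.

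**Row check (SAP 16.2.1, Early Stop column)**

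| Endpoint | No imputation | Imputed |
|---|---|---|
| Change in S/F by day | 14.2.2.1.1: Yes | 14.2.2.1.2: blank |
| Percentage change in S/F by day | 14.2.3.1.1: Yes | 14.2.3.1.2: blank |

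The imputed by-day plots go too, because no figures are produced.

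**Does any stated rule explain the blanks?** SAP 9.1.1.1 removes inference and figures. The imputed tables are neither; they are descriptive summaries of secondary endpoints, which that section says will be produced. Nor is imputation dropped in general. The kept trough summary (14.2.1.1) sets deaths by Day 14 to 0 (SAP 5.3.3.3), and the kept OSCI tables set death to 8 (SAP 5.3.3.4).

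**Size, on assumed inputs.** The documents give no death or discharge rates. Assume 20 per arm on one day, last S/F before discharge 430, and in-hospital S/F 200. Death = 0 comes from Table 5.

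| | Discharged | In hospital | Dead |
|---|---|---|---|
| EDP1815 | 15 | 4 | 1 |
| Placebo | 11 | 6 | 3 |

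- Table 5 mean, EDP1815: (15×430 + 4×200 + 1×0)/20 = 7250/20 = 362.5.
- Table 5 mean, placebo: (11×430 + 6×200 + 3×0)/20 = 5930/20 = 296.5.
- Difference: 362.5 − 296.5 = 66.0. If mean baseline is the same in both arms, the difference in mean change is also 66.0.
- No imputation: 200 on n = 4 against 200 on n = 6, difference 0.

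**Range.** A second set of assumptions uses baseline 300, so the changes are +150 at discharge (S/F 450), −80 in hospital (S/F 220) and −300 at death.

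| EDP1815 dead / discharged | Placebo dead / discharged | Imputed difference in mean change | Unimputed difference |
|---|---|---|---|
| 5% / 80% | 15% / 65% | 93.0 − 36.5 = +56.5 | 0 |
| 5% / 85% | 15% / 65% | 104.5 − 36.5 = +68.0 | 0 |
| 20% / 60% | 5% / 60% | 14.0 − 47.0 = −33.0 | 0 |
| 10% / 70% | 10% / 70% | 0 | 0 |

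For the first row, the EDP1815 figure is 0.05×(−300) + 0.80×150 + 0.15×(−80) = 93.0, and the others follow in the same way. The unimputed difference is 0 throughout because in-hospital values were set equal in the two arms. The examples show what the kept tables can miss; they do not predict what they would show.

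**The case against.** **Deaths and discharges are reported elsewhere.** A reader might infer that these participants disappear from the whole early-stop report. They do not. Trough S/F (14.2.1.1) includes deaths as 0 and discharged participants with their pre-discharge trough. OSCI (14.2.4.1), overall survival (14.2.5.1), ventilation-free survival (14.2.6.1), time to discharge (14.2.7) and data availability by inpatient or outpatient status (14.1.1.4) are also kept. Daily S/F values are listed (16.2.6.1). This stands and limits the point to the by-day S/F endpoints. It does not supply those two endpoints as Table 10 defines them.

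**Nothing is estimated after an early stop.** Table 10's summary measure is a difference in means, and an early-stop report tests and estimates no such difference. The kept tables are openly titled as unimputed, and at very small n a mean that mixes zeros with carried-forward values is hard to read. That is a fair reason to keep the unimputed tables. It does not explain omitting the imputed ones, which are equally descriptive.

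**Small cells print no mean.** SAP Section 12 shows only n, minimum and maximum when n is below 3. Very sparse days would therefore show no misleading mean, but they would say almost nothing about the endpoint.

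**The wrong direction.** A reader might also infer that the kept tables would reverse an effect. No reversal is shown here, and the documents contain nothing from which to derive one.

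**Scope.** SAP 9.1.1.1 speaks only of low recruitment, and the full analysis produces both versions. The endpoint wording also pairs Day 14 with the discharge day, so a discharge value might be placed there without imputation. That doubt does not reach Days 4, 7 and 10, or deaths.

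**Conclusion.** The point holds as a limited gap in the contingency output list, worth correcting. After a low-recruitment stop, the only by-day summaries of change and percentage change in S/F would describe participants alive and in hospital, contrary to Table 10 and to the SAP's own view of the missing data. The primary endpoint, the other secondary endpoints and the planned full analysis are unaffected.

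The size is not known. On the assumed inputs, a difference of 66 S/F units under the Table 5 rules appears as 0. Across the other mixes the hidden difference runs from −33.0 to +68.0, and it is nil when the arms have the same outcomes. These figures rest on assumed event rates and S/F values, and on in-hospital values set equal between arms.

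**What to change.** In SAP 16.2.1, set Early Stop to Yes for Tables 14.2.2.1.2 and 14.2.3.1.2, as descriptive summaries only. Keep Tables 14.2.2.1.1 and 14.2.3.1.1 alongside, and have them read with the numbers in hospital, discharged and dead by arm and day. Most of those counts already exist. OSCI Table 14.2.4.1 separates the three groups (scores 3–7, 0–2 and 8) at Days 4, 7 and 14, and Table 14.1.1.4 gives inpatient and outpatient availability on each day. Day 10 is not in the OSCI table and needs its own line.

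The cost is two cells in the output list and two more summary tables in an early-stop report. Both tables are already specified for the full analysis and use the existing Table 5 rules, so no new derivation or design change is needed.

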16.2.2 Figures

Figures will not be produced if the study is stopped early.

Number	Title	Population	Programming notes ¹
14.2.2.1.1	Mean (+/-SE) S/F Ratio by Day, No Imputation	ITT	DMC-Efficacy
14.2.2.1.2	Mean (+/-SE) S/F Ratio by Day, With Imputation Applied	ITT	DMC-Efficacy
14.2.2.2.1	Mean (+/-SE) Change from Baseline in S/F Ratio by Day, No Imputation	ITT	DMC-Efficacy
14.2.2.2.2	Mean (+/-SE) Change from Baseline in S/F Ratio by Day, With Imputation Applied	ITT	DMC-Efficacy
14.2.2.3.1	LS Mean (95% CI) Change from Baseline in S/F Ratio at Days 4, 7, 10 and 14	ITT	DMC-Efficacy
14.2.2.3.2	LS Mean (95% CI) Change from Baseline in S/F Ratio at Days 4, 7, 10 and 14, Sensitivity Analysis with No Imputation of S/F Ratio for Participants Who Die	ITT	DMC-Efficacy
14.2.2.3.3	LS Mean (95% CI) Change from Baseline in S/F Ratio at Days 4, 7, 10 and 14, Sensitivity Analysis Accounting for Use of New SOC	ITT	Only produced if a new SOC is introduced during the study
14.2.3.1.1	Mean (+/-SE) Percentage Change from Baseline in S/F ratio by Day, No Imputation	ITT	DMC-Efficacy
14.2.3.1.2	Mean (+/-SE) Percentage Change from Baseline in S/F ratio by Day, With Imputation Applied	ITT	DMC-Efficacy
14.2.3.2.1	LS Mean (95% CI) Percentage Change from Baseline in S/F ratio at Days 4, 7, 10 and 14	ITT	DMC-Efficacy
14.2.3.2.2	LS Mean (95% CI) Percentage Change from Baseline in S/F ratio at Days 4, 7, 10 and 14, Sensitivity Analysis with No Imputation of S/F Ratio for Participants Who Die	ITT	DMC-Efficacy
14.2.3.2.3	LS Mean (95% CI) Percentage Change from Baseline in S/F ratio at Days 4, 7, 10 and 14, Sensitivity Analysis Accounting for Use of New SOC	ITT	Only produced if a new SOC is introduced during the study
14.2.4.1	Histogram of WHO OSCI score at Days 4, 7, 14, 21 and 42	ITT	DMC-Efficacy
14.2.4.2	Proportion (95% CI) of Participants Remaining at or Below Their Baseline WHO OSCi Score at Days 4, 7, 14, 21 and 42	ITT	DMC-Efficacy
14.2.4.3	Histogram of Maximum WHO OSCI Score Reported	ITT	DMC-Efficacy
14.2.5	KM Curve of Overall Survival	ITT	DMC-Efficacy
14.2.6	KM Curve of Intubation and Mechanical Ventilation Free Survival	ITT	DMC-Efficacy
14.2.7	Cumulative Incidence Function of Time to Discharge	ITT	DMC-Efficacy

Number	Title	Population	Programming notes ¹
14.2.8	Cumulative Incidence Function of Time to SpO ₂ ≥94% Without Further Requirement for Oxygen Therapy	ITT	DMC-Efficacy
14.2.9	Cumulative Incidence Function of Time to Recovery from Onset of Symptoms	ITT	DMC-Efficacy
14.2.10	Mean (+/-SE) Maximum Temperature by Day	ITT	DMC-Efficacy
14.2.11	Mean (+/-SE) SpO ₂ by Day	ITT	DMC-Efficacy

16.3 Safety

16.3.1 Tables

Number	Title	Population	Early Stop	Programming notes ¹
14.3.1.1.1	Summary of All TEAEs by System Organ Class and Preferred Term	Safety	Yes	DMC-Unblinded
14.3.1.1.2	Summary of Treatment Phase TEAEs by System Organ Class and Preferred Term	Safety	Yes	DMC-Unblinded
14.3.1.1.3	Summary of Follow-up Phase TEAEs by System Organ Class and Preferred Term	Safety	Yes	DMC-Unblinded
14.3.1.1.4	Summary of All TEAEs by Age Group, System Organ Class and Preferred Term	Safety		DMC-Safety Only produced if participants aged >65 are permitted to enter the study
14.3.1.2	Summary of Treatment-Related TEAEs by System Organ Class and Preferred Term	Safety	Yes	
14.3.2.1	Summary of Serious TEAEs by System Organ Class and Preferred Term	Safety	Yes	DMC-Unblinded
14.3.2.2	Summary of TEAEs Leading to Permanent Discontinuation from Study Drug by System Organ Class and Preferred Term	Safety	Yes	
14.3.2.3	Summary of TEAEs Leading to Withdrawal from the Study by System Organ Class and Preferred Term	Safety	Yes	
14.3.2.4	Summary of Fatal TEAEs by System Organ Class and Preferred Term	Safety	Yes	

Number	Title	Population	Early Stop	Programming notes ¹
14.3.2.5.1	Summary of TEAEs of Special Interest by Preferred Term and CTCAE Grade	Safety	Yes	DMC-Unblinded
14.3.2.5.2	Summary of TEAEs of Special Interest by Preferred Term and Relationship to Study Drug	Safety	Yes	DMC-Unblinded
14.3.4.1.1	Summary of Change from Baseline in Hematology	Safety	Yes	
14.3.4.1.2	Summary of Shifts from Baseline to Worst-case Post-Baseline with Respect to the Normal Range in Hematology	Safety	Yes	DMC-Unblinded
14.3.4.1.3	Summary of Shifts from Baseline to Worst-case Post-Baseline with Respect to the PCI Criteria in Hematology	Safety	Yes	DMC-Unblinded
14.3.4.1.4	Summary of Shifts from Baseline to Worst-case Post-Baseline with Respect to the PCI Criteria in Hematology, by Age Group	Safety		DMC-Safety Only produced if participants aged >65 are permitted to enter the study
14.3.4.2.1	Summary of Change from Baseline in Clinical Chemistry	Safety	Yes	
14.3.4.2.2	Summary of Shifts from Baseline to Worst-case Post-Baseline with Respect to the Normal Range in Clinical Chemistry	Safety	Yes	DMC-Unblinded
14.3.4.2.3	Summary of Shifts from Baseline to Worst-case Post-Baseline with Respect to the PCI Criteria in Clinical Chemistry	Safety	Yes	DMC-Unblinded
14.3.4.2.4	Summary of Shifts from Baseline to Worst-case Post-Baseline with Respect to the PCI Criteria in Clinical Chemistry, by Age Group	Safety		DMC-Safety Only produced if participants aged >65 are permitted to enter the study
14.3.5.1	Summary of Change from Baseline in Vital Signs	Safety	Yes	
14.3.5.2	Summary of Shifts from Baseline to Worst-case Post-Baseline with Respect to the PCI Criteria in Vital Signs	Safety	Yes	DMC-Unblinded

Number	Title	Population	Early Stop	Programming notes ¹
14.3.5.3	Summary of Shifts from Baseline to Worst-case Post-Baseline with Respect to the PCI Criteria in Vital Signs, by Age Group	Safety		DMC-Safety Only produced if participants aged >65 are permitted to enter the study

